2.4.4.3.1 Free-flap survival rate at 30 days

As per section 2.1.3.5.1 each flap for each patient in the FAS will be assigned to 'Yes' or 'No' for free flap survival at 30 days. This represents a binary outcome. The analysis of this variable is at the procedure (flap) level. Summary and analysis will be as described above for flap loss/failure (Model 4).

Sponsor: MMI Product: Symani system for microsurgical anastomosis Study: PRIMO	
Statistical Analysis Plan Final 22 November 2024	

In addition, the effectiveness of the Symani System will be evaluated for consistency with the free flap success rates reported in the UK National Flap Registry [1], where the overall free flap survival rate was 96.0% (95% confidence limits, 95.4%, 96.6%)."

2.4.4.3.2 Intraoperative anastomosis patency

As per section 2.1.3.5.2, each robotic anastomosis conducted on each patient in the FAS during their index procedure will be assigned to 'Yes' or 'No' for intraoperative anastomosis patency. This represents a binary outcome at the anastomosis level.

Methods for summarization and analysis will be as described for the primary effectiveness endpoint (Model 1/1a).

2.4.5 Analyses of questionnaire data

All questionnaire results will be summarized using frequency tables, where the number (and percentage) of respondents selecting each response option will be presented by question.

In addition, the number of positive responses per questionnaire and the percentage of positive responses (see section 2.1.4 for derivation) will be presented using descriptive statistics. The number of missing responses per questionnaire will also be presented.

2.4.6 Analyses of safety data

2.4.6.1 General analyses of adverse events

Summary tables displaying both incidence and number of adverse events (AE) overall, by severity, by relationship to study device, by relationship to study procedures, and by seriousness will be produced. The incidence of AE which are device deficiencies will also be shown. Subset incidence tables will be produced for anticipated AE, and for unanticipated AE.

The overall incidence of any adverse event will be presented with exact 95% confidence limits. The result will be compared descriptively with the 30 day complication rate of 31.6% (95% confidence limits 27.5, 36.0%) reported by Veith et al [2]. The paper by Veith et al has been selected as the literature value for descriptive comparison as it describes complication rate in the 30 day post-operative period; which is the period of observation in the current study. Other than this paper there is limited published information on 30 day complication rates.

For serious AE, frequency tabulations of the reasons for the event being an SAE will be produced. A subset incidence table will be produced for anticipated SAE, and a second subset table for unanticipated SAE.

Tables will be produced for the SAS and by subpopulation (prospective/retrospective).

Sponsor: MMI Product: Symani system for microsurgical anastomosis Study: PRIMO	
Statistical Analysis Plan Final 22 November 2024	

All adverse event data will be shown in patient data listings.

Sponsor: MMI Product: Symani system for microsurgical anastomosis Study: PRIMO	
Statistical Analysis Plan Final 22 November 2024	

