1.3.2 Safety endpoints

The complications as indicated above, will be collected as adverse events (AE, SAE/ADE/SADE/ADE/DD) reported by patients or evaluated by the Surgeon from day 0 to either 30 days after surgery for free flaps, replantation and other procedures, or 24 weeks after surgery for the LVA procedures will be recorded.

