2.1.3.1 Primary effectiveness endpoint – Procedure Robotic Success

Form R or Anastomosis Data Form will be completed for each anastomosis. If the answer to the question 'How did you intend to perform this anastomosis' is 'Robotic' then the anastomosis is included for this endpoint.

The endpoint will be derived for each anastomosis using the question "Did you experience any system technical issues resulting in unplanned return to conventional suturing".

If the response is 'No' and the number of robotic sutures is > 0 or the number of robotic redo sutures is > 0, the anastomosis will be classified as 'intra-operative change from robotic to manual' = 'no'.

If the response is 'yes' anastomosis will be classified as intra-operative change from robotic to manual = 'yes'.

If there is no response to the question the anastomosis classification will be missing.

If the planned approach was manual the result will be N/A

The unit of analysis for this endpoint is the anastomosis.

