2.1.5 Safety endpoints

All adverse events (AE, SAE/ADE/SADE/ADE/DD) reported by patients or evaluated by the Surgeon from day 0 to either 30 days after surgery for free flaps, replantation and other procedures, or 24 weeks after surgery for the LVA procedures will be recorded.

All adverse events will be recorded on an adverse event form in the CRF (form U2 in Dendrite or Repeating Data: Adverse Events in Castor). Adverse events will be coded using MedDRA to obtain system organ class (SOC) and preferred term (PT).

All events are assessed by the surgeon for severity (mild/moderate/severe) and seriousness (serious/not serious). In addition, for each event, the surgeon will answer three questions regarding relationship to the device:

- Related to the device
- Related to device malfunction
- Related to device misuse

For each of these assessments, the response is on a 5 point 'scale', namely:

- Not related
- Unlikely
- Possible
- Probable

Sponsor: MMI Product: Symani system for microsurgical anastomosis Study: PRIMO	
Statistical Analysis Plan Final 22 November 2024	

- Definite OR
- Unassessable

They are also asked to note whether there was a different (not device related) cause.

Treatment initiated (if any) and outcome (resolved, resolved with sequelae, ongoing or death) are also recorded.

Event details are recorded as verbatim text.

A separate form will be completed for each event.

Adverse events of special interest, namely, the AEs cited in the literature (e.g., arterial insufficiency, venous congestion) will be flagged based on MedDRA coding.

No further derivations of adverse events data will be undertaken.

2.1.5.1 Additional safety endpoints not defined in the protocol.

2.1.5.1.1 Freedom from device related serious adverse events prior to discharge.

Dendrite's Form U2, and Castor's Repeating Data Form: Adverse Events, is used to collect adverse event data. If there are any adverse events marked as serious where ANY device related question (see note below) is 'possible', 'probable' or 'definite' the event will be classified as a device related SAE = yes.

If ALL AE forms have full responses to the required questions and the AE is not classified as 'device related SAE'=yes then the patient will be classified as device related SAE=No.

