2.2.3 Safety populations

2.2.3.1 Safety Analysis Set (SAS)

The SAS will include all patients in the AES that had at least one robotic suture placed or attempted. Note that this definition will include all patients in the FAS as well as any other patients outside of this set (but in the All Enrolled Set) where robotic anastomosis is attempted but no robotic sutures placed. To classify as 'robotic anastomosis attempted' there will be a robotic time recorded on the CRF for at least one anastomosis.

As for the SAS, two sub-populations will be defined based on the SAS.

- The prospective patient sub-population
- The retrospective patient sub-population.

All summaries and analyses will be presented using all data combined and by sub-population.

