2.4.4.1 Analysis of primary effectiveness variable – procedure robotic success

As per section 2.1.3.1 each anastomosis for each patient in the FAS will be assigned to ‘Yes’ or ‘No’ for procedure robotic success. This represents a binary outcome. The analysis of this variable is at the anastomosis level.

For each surgery type (replantation, free flap or lymphatic surgery) stratified frequency tables will be presented stratified by subpopulation (prospective/retrospective) and recipient site/location. The denominator is the number of anastomoses. The proportion of anastomoses classified as a robotic success by stratum and overall for each surgery type will be presented with 95% confidence limits. Results will also be presented on a forest plot.

For replantations a further stratifying variable will be included, namely procedure type (free/nerve).

For each surgery type, a generalized linear mixed model (GLMM) will be used to estimate the percentage of anastomoses classified as robotic success. In SAS, PROC GLIMMIX will be utilized to analyze the data. Subpopulation (prospective/retrospective), recipient site/location and surgeon experience will be included as fixed effects, and surgeon as a random effect. Procedure number (within a surgery type) and anastomosis number (within a procedure) will be included as random terms to acknowledge the dependence in the data (see note above). From the model the adjusted rate of robotic success will be obtained, with 95% confidence limits, for each type of surgery overall and by recipient site/location, by surgeon experience and by subpopulation. (Model 1).

Fixed effects

For free flaps, recipient site will be head and neck, extremities, breast or other.

For lymphatic surgery location will be heads and neck, upper limbs or lower limbs

For replantations there will also be a factor for procedure type (free or nerve), as well as recipient site (as for free flaps) (Model 1a) and results also obtained by procedure type (free/nerve).

For all types of surgery, surgeon experience is classified as microsurgeon, fellow, resident.

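### The only planned device-deficiency result rests on adverse event records and is not linked to the recorded technical failures, so it may be understated; failures in safety-set patients outside the FAS can escape both analyses

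*SAP*

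**What the plan says.** The safety analysis (SAP 2.4.6.1) is run on the SAS. Its one statement on device deficiencies is "The incidence of AE which are device deficiencies will also be shown". The same section compares the overall incidence of any AE descriptively with a published 30-day complication rate of 31.6% (95% limits 27.5% to 36.0%).

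On collection, SAP 2.1.5 speaks of "All adverse events (AE, SAE/ADE/SADE/ADE/DD) reported by patients or evaluated by the Surgeon from day 0", and SAP 1.3.2 says that complications "will be collected as adverse events (AE, SAE/ADE/SADE/ADE/DD) reported by patients or evaluated by the Surgeon". DD is thus listed inside the adverse-event umbrella. Section 2.1.5 adds that "All adverse events will be recorded on an adverse event form in the CRF", asks for each event whether it is "Related to device malfunction", and rules out further derivations of AE data. DD is not in the abbreviation list and is defined nowhere in the SAP.

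Technical failures are also captured elsewhere. For every anastomosis intended as robotic, the primary endpoint (SAP 2.1.3.1) uses the question "Did you experience any system technical issues resulting in unplanned return to conventional suturing", asked regardless of harm. For its analysis (SAP 2.4.4.1), "each anastomosis for each patient in the FAS will be assigned" a result. The SAS (SAP 2.2.3.1) is wider than the FAS: it also takes in patients "where robotic anastomosis is attempted but no robotic sutures placed", provided a robotic time was recorded.

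**The concern.** The study's stated objective is to monitor the safety, usability, performance and long-term efficacy of the device. A technical failure that is finished by hand without injury is a performance event, but it is not obviously an adverse event. If the only DD figure is drawn from AE records, and nobody checks it against the technical-issue answers, the safety section could report few or no deficiencies while the study's own anastomosis forms document failures.

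The primary endpoint picks up such failures in FAS patients. It does not do so for patients in whom the robot was tried but no anastomosis was classed as robotic. Those may be the most complete failures in the study.

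**Working it through.** The documents give no DD rate, count or threshold, so there is no figure to reproduce. The check sets the sections side by side.

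**1. What the DD line counts.** The text allows two readings.
- AE keeps its usual meaning of harm. A deficiency without harm is then outside the line.
- AE means the umbrella of 1.3.2 and 2.1.5, which includes DD. A deficiency without harm can then be entered on the AE form and counted. It may then also enter the overall AE incidence that is set against 31.6%, which is a complication rate.

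The SAP does not choose between them, and each reading leaves something to correct.

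**2. Whether the technical-issue answers feed the line.** They do not. Section 2.1.3.1 uses them only for the primary endpoint, and 2.1.5 allows no further derivation of AE data. A Yes reaches the DD line only if the surgeon also completed an AE form. No reconciliation is planned, and retrospective data are collected as available (SAP 1.1).

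**3. Where a technical failure is counted, by patient.** FAS entry (SAP 2.2.2.1) needs at least one anastomosis classed as robotic. That means one or more robotic sutures or, if the suture count is missing, robotic intent together with a No to the technical-issue question.

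| Patient | Primary analysis | DD line |
|---|---|---|
| In FAS | Yes, at anastomosis level | Only with an AE form |
| In SAS, not FAS (robotic time recorded, no anastomosis classed as robotic) | No | Only with an AE form |
| Enrolled, no robotic suture and no robotic time recorded | No | No (outside the SAS) |

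Where the suture count is missing, a Yes is itself what stops the anastomosis being classed as robotic. If the patient has no other robotic anastomosis, the failure removes the patient from the FAS.

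**4. Scale, by assumption only.** Take N = 402 (the planned minimum, used here in place of the unknown SAS size), an assumed true number of patients with a DD, and an assumed share of them whose DD is also an AE record.

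Reported incidence = (true number × share) / 402. For example, 20 × 0.50 = 10, and 10/402 = 2.5%.

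| True DD patients (exact 95% limits) | Share 0% | 25% | 50% | 100% |
|---|---|---|---|---|
| 8 = 2.0% (0.9 to 3.9) | 0.0% | 0.5% | 1.0% | 2.0% |
| 20 = 5.0% (3.1 to 7.6) | 0.0% | 1.2% | 2.5% | 5.0% |
| 40 = 10.0% (7.2 to 13.3) | 0.0% | 2.5% | 5.0% | 10.0% |

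The documents fix neither the row nor the column. The understatement runs from none (last column) to complete (first column).

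**The case against.** The strongest reply is that the SAP uses adverse events as an umbrella that names DD and sends everything under it to the AE form. On that usage the sentence in 2.4.6.1 means the DD records on that form, harmful or not, and nothing is lost. This stands as a possible reading. A reader might infer that harmless failures are left out and that the DD incidence is too low; the documents show only that this could happen. The case report forms, the retrospective addendum and the full protocol text beyond the synopsis are not available, so a separate DD field cannot be ruled out. Section 2.1.5.1.3 does indicate that the Dendrite AE form can carry separate dates for an AE and an adverse device effect.

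Second, harmless conversions are already analysed as the primary endpoint, and Appendix 1 also lists a rate of intra-operative approach change. FAS entry is by patient, so an abandoned anastomosis still counts if the patient had another one classed as robotic. This is correct for FAS patients. But these are anastomosis-level effectiveness results, 2.2.2.1 makes the FAS the basis of all effectiveness analyses, and SAS patients outside the FAS remain uncovered.

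Third, section 2.4.3 promises summaries of anastomosis data and listings. It names no population, and the anastomosis items described in 2.1.2 do not include the technical-issue question, so it cannot be relied on to fill the gap.

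Fourth, no planned conclusion depends on the DD line, which has no threshold or comparator. That limits the consequence but does not remove it in a device-monitoring study.

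**Conclusion.** The point holds in a limited form. The only planned DD result is worded as a subset of AEs, DD is undefined, and no rule connects that result to the technical-issue answers. The incidence **may** be understated, and the size cannot be determined from the documents.

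The firm part is narrower. For an SAS patient with no anastomosis classed as robotic, a technical failure enters no named effectiveness or safety analysis unless an AE form was also completed. This follows from the set definitions alone. How many such patients there will be is not stated.

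A reader might be tempted to size the problem from the planning success rate of 89%, that is 402 × 0.11 = 44 failures. The documents do not support this. The 89% is the alternative used for the power statement, set against a literature failure and complication rate; it is not a forecast of technical-issue answers. Nor does the SAP equate each such answer with a device deficiency.

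The change is worth making because it alters a reported result and draws on data that the forms already collect.

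**What to change.** In SAP 2.4.6.1, define DD, say where a deficiency without harm is recorded, and replace the DD sentence with text along these lines:

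> Device deficiencies will be counted in the SAS whether or not harm occurred. Two sources will be tabulated separately: (a) AE-form records classed as DD, split into with and without harm; (b) anastomoses, and patients, with a Yes to the system technical issue question, including SAS patients outside the FAS. The number of patients with at least one of either will be given, each patient counted once, with exact 95% confidence limits. Deficiencies without harm will not contribute to the overall AE incidence that is compared with the published 31.6%. Technical-issue answers will be listed for the All Enrolled Set.

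Keeping the sources apart avoids relabelling every technical issue as a DD. Counting patients once avoids having to match individual anastomosis forms to AE forms. The All Enrolled Set listing makes visible any recorded failure that occurred before a robotic time was entered.

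The cost is SAP wording, one extra table and one listing. If the AE form has no field that separates deficiencies with and without harm, the split will need a review of the verbatim event text. The reported device-failure figure may become less favourable.

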2.4.6.2.3 Re-admission within 30 days

As per section 2.1.4.1.3, each patient in the SAS will be assigned to 'Yes' or 'No' for re-admission and the time to re-admission derived.

Patients classified as re-admission = "Yes" will be classified as events, and other patients will be censored. A Kaplan Meier plot will be produced for time to re-admission, overall, by subpopulation (prospective/retrospective) and by procedure type (flap, replantation, lymphatic). From the Product Limit Estimator (PL estimator), an estimate of re-admission rate within 30 days will be obtained.

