2.5.5 Windows for time points

All data are expected to be collected within a timeframe of 30 \pm 7 days from the initial study procedure (or 24 weeks \pm 2 weeks for lymphatic surgery). If a patient has a revision procedure where the revision is to a robotic anastomosis, then the timeframe for data collection will be 30-days from the date of the last revision procedure (revision to a robotic anastomosis), where the date of re-operation is prior to the date of discharge. However, for the retrospective data collection, available data will be used whenever possible. Data may not be available at 30 days post-operation.

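### The any-AE rate compared with a 30-day literature figure has no day-30 cut-off and no rule for incomplete follow-up, so it is not a 30-day rate and may err in either direction

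*SAP*

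**What the plan says.** **Estimator and comparison (SAP 2.4.6.1).** "The overall incidence of any adverse event will be presented with exact 95% confidence limits". The next sentence reads: "The result will be compared descriptively with the 30 day complication rate of 31.6% (95% confidence limits 27.5, 36.0"%). The literature source is preferred because it covers 30 days after surgery, "which is the period of observation in the current study". The tables are to be shown on the safety set: "Tables will be produced for the SAS and by subpopulation (prospective/retrospective").

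**Denominator (SAP 2.2.3.1).** "The SAS will include all patients in the AES that had at least one robotic suture placed or attempted". No minimum follow-up is required.

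**Collection window (SAP 1.3.2 and 2.1.5).** AEs run from day 0 to 30 days for flaps, replantations and other procedures, "or 24 weeks after surgery for the LVA procedures will be recorded". Section 2.1.5 rules out further derivations of AE data, so nothing restricts the numerator to the first 30 days.

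**Incomplete follow-up.** For retrospective patients, SAP 2.5.5 warns: "Data may not be available at 30 days post-operation". SAP 2.5.6 expects missing data in that group, and SAP 1.7 counts those patients towards the 402. SAP 2.5.2 excludes a patient from any analysis whose outcome cannot be determined. It does not say when that applies to the occurrence of any AE.

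**The other 30-day safety rates.** For re-admission (SAP 2.4.6.2.3), patients with the event "will be classified as events, and other patients will be censored", and the rate is read from the product-limit curve at 30 days. Re-operation (2.4.6.2.4) and death (2.4.6.2.5) are handled in the same way.

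**The concern.** A simple proportion estimates a 30-day risk only if every patient is observed to day 30 and nothing later is counted. The SAP secures neither condition.

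The AE forms are event-driven, with one form per event. A patient who withdraws on day 3 without an event, or a retrospective patient whose record stops at discharge, leaves no empty field to flag. That patient can sit in the denominator as though observed for 30 days. In the other direction, a lymphatic patient whose first AE comes in month 3 enters the numerator of a figure that is set beside a 30-day rate.

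This is the study's overall complication rate, and a reader will judge it against an interval whose lower limit lies only 4.1 points below its estimate (31.6 - 27.5). The prospective and retrospective columns will also be read side by side although their observation times may differ. The SAP gives no reason for leaving this rate outside the method it uses for its other 30-day safety rates.

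**Working it through.** **1. The plan's own figure.** The SAP gives no numerator or denominator for 31.6%, so it cannot be re-derived. As a consistency check, I looked for counts that reproduce 31.6% (27.5 to 36.0%). Clopper-Pearson limits fit counts from 149/471 to 155/490, and Wilson limits fit 143/453 to 146/462. The figure is coherent and is used below as an assumed true 30-day risk, T = 0.316.

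**2. Scale.** With 402 patients and 127 events (31.6%), the exact limits are 27.1% to 36.4%, a width of 9.3 points.

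**3. Early exit.** Let f be the fraction without full 30-day observation and c the share of their 30-day first events still captured. Neither is in the documents, except a 5% dropout in the protocol synopsis. Incompleteness is assumed unrelated to risk.

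- Reading A, no AE form means no event: rate = T × [1 - f(1 - c)]
- Reading B, SAP 2.5.2 removes incomplete patients who have no AE: rate = T × [1 - f(1 - c)] / [1 - f(1 - Tc)]

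Example with f = 0.20 and c = 0.75:

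- A = 0.316 × 0.95 = 30.0%
- B = 0.3002 / [1 - 0.20 × (1 - 0.237)] = 0.3002 / 0.8474 = 35.4%

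| f | c | Reading A | Reading B |
|---|---|---|---|
| 5% | 0 | 30.0% | 31.6% |
| 5% | 0.5 | 30.8% | 32.2% |
| 5% | 0.75 | 31.2% | 32.4% |
| 20% | 0 | 25.3% | 31.6% |
| 20% | 0.5 | 28.4% | 34.2% |
| 20% | 0.75 | 30.0% | 35.4% |
| 40% | 0 | 19.0% | 31.6% |
| 40% | 0.5 | 25.3% | 38.1% |
| 40% | 0.75 | 28.4% | 40.9% |

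Across c = 0 to 0.75, reading A lowers the rate by 0.4 to 1.6 points at 5%, 1.6 to 6.3 at 20%, and 3.2 to 12.6 at 40%. Removing every incomplete patient, with or without an AE, would leave 31.6%.

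**4. Late lymphatic events.** Let L be the lymphatic share and q the risk of a first AE between day 30 and week 24 among those event-free at day 30. Both are assumed. T is taken as equal across surgery types, and late events as fully captured. The addition to the rate is L(1 - T)q.

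- L = 40%, q = 10%, complete follow-up: 0.316 + 0.40 × 0.684 × 0.10 = 34.3%
- The same with f = 20%, c = 0.5 under reading A: 0.2844 + 0.0274 = 31.2%
- The same with q = 20%: 0.2844 + 0.0547 = 33.9%

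**5. Where the two cancel.** Under reading A, q = f(1 - c)T / [L(1 - T)]. At L = 40% and c = 0.5 this is 2.9% for f = 5%, 11.5% for f = 20% and 23.1% for f = 40%. Plausible inputs lie on both sides of the break-even.

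**The case against.** A reader might infer that the reported rate will be too low against 31.6% and so flatter the device. The documents do not support that. Truncation lowers the rate only under reading A, which the SAP does not state. Its one general rule, in 2.5.2, speaks of exclusion and could raise the rate. Collection to 24 weeks for lymphatic surgery raises it too, as does the extended window after an in-hospital revision in 2.5.5. This part of the objection stands in full.

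Reading A is still the natural one. The AE endpoint with an explicit negative rule (SAP 2.1.5.1.1) classes a patient as negative when all existing AE forms are complete and none qualifies, and a patient with no forms meets that condition.

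The large effects also need assumed fractions. At the only documented dropout, 5%, the loss is at most 1.6 points. But that figure belongs to Protocol Rev. 03 of August 2022, and the retrospective addendum was approved in December 2022. It therefore does not bound incompleteness in the retrospective group.

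There are safeguards. The comparison is descriptive, with no test. The tables are split by subpopulation, and SAP 2.4.1 and 2.5.6 require missing data to be shown. These limit the harm. However, a patient without an AE form need not register as missing, so the missing counts may not reveal the problem.

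Nor is this the only result with an outside benchmark: re-operation is set against 10.7% (2.4.6.2.4) and flap survival against 96.0% (2.4.4.3.1). Re-operation already has a product-limit estimate, which shows that the method is at hand.

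Finally, a product-limit estimate cannot recover events left unrecorded during observed time, and the comparator may itself be a simple proportion. Both points are fair and limit what the change can achieve.

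**Conclusion.** The point holds as a defect of definition. The any-AE incidence has no 30-day window and no rule for incomplete follow-up, so it does not estimate what the literature figure describes. SAP 2.4.6.1 calls 30 days the study's period of observation, while 1.3.2 and 2.1.5 collect to 24 weeks after lymphatic surgery; these statements must be reconciled.

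The net direction is open. The sizes for early exit rest on an assumed true risk of 31.6%, on incompleteness unrelated to risk, and on reading an absent AE form as no event. The fractions at 20% and above are illustrations, as are the lymphatic share and late-event risk. Two opposing errors might cancel by chance, but that would not make the comparison sound.

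Because the comparison is descriptive and carries no success criterion, this is an inexpensive improvement and not a threat to the study's main conclusion. It does not resolve the difference in content: the numerator is any AE across all surgery types, whereas the cited source, by its title, concerns complications of lower-extremity free flaps.

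**What to change.** Add to SAP 2.4.6.1, for the literature comparison only:

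> Time to first AE will be analysed by the product-limit method in the SAS. Patients without an AE will be censored at their last actual assessment for AEs. The estimated risk at day 30, with 95% confidence limits, will be compared descriptively with the literature rate, overall and by subpopulation, with the number still at risk at day 30.

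Four details need stating:

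- **Censoring date.** SAP 2.1.5.1.3 to 2.1.5.1.5 take the latest date on any form, including protocol deviation forms. A deviation date need not be an assessment, so the last visit or contact at which AEs were assessed is safer here.
- **Visit window.** The 30 ± 7 day window in 2.5.5 allows a final visit from day 23, which would censor some completers before day 30. Numbers at risk at day 23 should be shown as well.
- **Crude table.** Keep it as description, labelled with its actual collection periods, and say how 2.5.2 applies to it.
- **Period of observation.** Reconcile the wording in 2.4.6.1 with 1.3.2 and 2.1.5.

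The cost is a few sentences and one further estimate. AE onset dates and follow-up dates are already used elsewhere in the SAP. The headline rate may move either way. The estimate still assumes that censoring is unrelated to risk, so the prospective figure should be read alongside the combined one.
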